The PILLAR study protocol, under which subjects were enrolled, limited catheter in-dwelling time to 36 hours and total pump time (therapy time) to 24 hours. As can be seen in the table above, the average pump time was shorter than anticipated with only one subject receiving the complete 24 hour allotted time for study therapy. Despite this, clearance of red blood cells (RBCs) from the lumbar cistern was seen as noted in the table below. Longer pump times will be necessary for more complete blood clearance. Pre and Post-Neurapheresis total protein measures were also taken to account for removal of by-products from lysed blood.

PILLAR Post-Neurapheresis Outcomes

Outcome Measured N=13	Pre-Neurapheresis mean \pm STD	Post-Neurapheresis mean \pm STD	Percent Decrease of Means
Concentration of Total Protein	537.36 \pm 500.70 mg/dL	144.09 \pm 188.44 mg/dL	73.2%
Concentration of CSF Red Blood Cells (RBCs)	2.78e5 \pm 2.43e5 cells/ μ L	1.17e5 \pm 1.30e5 cells/ μ L	57.9%

Subjects were followed at 2-weeks and 30-days post-Neurapheresis. Other notable outcomes include; a mean of 12 days to discharge from the Neuro ICU with a range of [6 – 18 days]. By the 2-week visit, 38.5% (5/13) were discharged home which increased to 69.2% (9/13) by 30 days.

PILLAR Follow-up Outcomes

Follow-up Status N=13	Two Week Median [range]	30 Day Median [range]
GCS	15 [11-15]	NR*
WFNS	1 [1-5]	NR*
mRS	2 [1-5]	1 [0-4]
GOS	NR*	5 [3-5]
Barthel	NR*	100 [20-100]

*These neuro assessments were not required per protocol

Finally, the primary safety endpoint for the study was the assessment of adverse events associated with the placement of the catheter and operation of the system. As there were no (0) adverse events associated with the placement of the catheter and minimal, expected, non-serious adverse

events (as seen below) during Neurapheresis, the end points of this study were considered to have been met.

The adverse events (AEs) reported below is site reported and was also reviewed by the independent DSMB. While the AEs were reported as potentially related to Neurapheresis therapy, they are also known AEs for subarachnoid hemorrhage patients.

PILLAR Device or Procedure Related Adverse Events During Neurapheresis

Event	Timeframe	Serious Adverse Event (SAE)	Related to System	Related to Neurapheresis	n/N (%)
Headache with Vomiting	Neurapheresis	No	No	Yes	1/13 (7.7%)
Vomiting	Neurapheresis	No	No	Yes	1/13 (7.7%)

PILLAR Device or Procedure Related Adverse Events After Neurapheresis

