5.2 Screening and Subject Enrollment

Screening for potential study subjects can be done either prior to or after aneurysm securement depending on the institutional work flow, IR/OR availability, LAR availability or patient status. Inclusion or exclusion criteria that can be assessed by institutional SOC may be done so prior to written informed consent, however no study specific procedures may be performed until informed consent is obtained. Informed consent is considered the point of enrollment.

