7.1 Screening Requirements

Standard of care assessments may be used to screen potential subjects against inclusion/exclusion (I/E) criteria for the study. Testing that is outside of SOC, cannot be performed until after a subject has been enrolled (i.e. written informed consent obtained). Once the subject has been enrolled and it has been determined that screening criteria are met, the subject can be prepared for catheter placement. If instead it is determined that a subject no longer meets study criteria after completing all screening assessments, they are to be withdrawn immediately and classified as an “Intent to Treat” subject. Enrollment data collected to that point and the reason for study exit should be entered into the case report forms for submission to the sponsor.

A screening CT is required to assess I/E criteria and is expected to be a SOC test for the diagnosis and treatment planning of aSAH. If a subject has been transferred from another institution at which a CT was obtained, a new screening CT is not required provided that an electronic copy of the CT can be obtained from the referring institution. It is expected that the volume of any identified mass lesions as noted in the study exclusion criteria will be calculated using the standard of care formula used by most radiologists in practice today. The formula should be based on the estimated volume of an ellipsoid ($L \times W \times H \times 0.52$ (where 0.52 is an approximation for $\pi/6$).

Volume = $A \times B \times C / 2$

- A = greatest hemorrhage diameter in the axial plane
- B = hemorrhage diameter at 90° to A in the axial plane
- C = originally described as the number of CT slices with hemorrhage multiplied by the slice thickness, but can simply be substituted with the craniocaudal diameter of the hemorrhage where there is access to multiplanar reformats

A venous blood sample is also required for screening and to establish baseline values for certain inflammatory markers (platelets and white blood cells including neutrophils and lymphocytes). Sample amounts should be based on site specific laboratory requirements for completion of tests including a Complete Blood Count (CBC) with Differentials and a Comprehensive Metabolic Panel (CMP). Current laboratory certificates are required by the sponsor with laboratory processes to be made available upon request.

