7.5.7 CSF Sampling During Neurapheresis

During catheter in-dwelling and Neurapheresis therapy, CSF samples will be obtained at regular intervals until the catheter is removed. A maximum of 11 CSF samples total per subject will be taken. Ten of those during catheter indwelling, though fewer may be taken if the catheter must be removed early.

Samples will be taken according to the schedule in Table 10 below. The initial CSF sample will be taken during catheter placement however, the first sample taken during catheter in-dwelling will be considered the Baseline CSF sample (pre-Neurapheresis sample) to which the later samples will be compared. The last CSF sample taken will be considered the Final sample or (post-Neurapheresis sample) which will be compared to the Baseline sample for applicable endpoint analyses. To account for different assay requirements, CSF sample volumes are different for the initial and seventh (40 hr) sample than those in between.

It is allowable to collect less CSF sample volume for completion of the Cell counts with Differentials based on site specific laboratory requirements. Current laboratory certificates are

required by the sponsor with laboratory processes to be made available upon request. Care should be taken to ensure laboratory samples are handled and processed consistently for accurate data reporting.

During catheter in-dwelling, the first sample (#2 on Table 10 below) should be taken after 1 hour ($\pm 30\text{min}$) of Neurapheresis therapy. The MNeuro CFS will assist in monitoring the therapy time in order to prepare for the sample. The next CSF sample should be taken at 8 hours ($\pm 2\text{hr}$) from catheter securement (8 hours of catheter in-dwelling) then each subsequent sample taken every 8 hours ($\pm 1\text{hr}$) from the previous scheduled sample (i.e. every 8 hours during catheter in-dwelling).

Table 3: Required CSF Samples

Sample #	Sample Metric	Required Assay	CSF Sample Volume
1	During Catheter Placement (needle stick)	Cell counts with Differential: RBC, WBC, neutrophils, lymphocytes, etc. Chemistries: Total protein, Glucose, Culture	3ml
		CSF Biomarkers (requires -80° storage until shipped) ^β	2ml ^β
2	1hr ($\pm 30\text{min}$) of Neurapheresis	Cell counts with Differential and Chemistries	3ml
3	8hr ($\pm 2\text{hr}$)*	Cell counts with Differential and Chemistries	3ml
4	16hr ($\pm 2\text{hr}$)*	Cell counts with Differential and Chemistries	3ml

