7.5.8 Additional Testing Requirements During Neurapheresis

At 36 hours (± 4 hr) and 72 hours (± 4 hr) or end of catheter in-dwelling (whichever comes first), a venous blood sample and CT are required. Timing should be aligned with a study require neuro check for efficiency. The 36 hour CT and the 72 hour (end of catheter in-dwelling) CT must be obtained using a department scanner at optimal metal artifact reduction settings as it will be used for primary endpoint analysis. The 72 hours (± 4 hr) or end of catheter in-dwelling CT can be obtained after catheter removal to minimize the risk of compromising sterility of the fluid loop. However, if it obtained prior to catheter removal, steps to maintain sterility during patient transport should be followed as described in 7.5.9 below.

The venous blood sample should be submitted for a Complete Blood Count (CBC) with Differentials and a Comprehensive Metabolic Panel (CMP) to allow for comparison to pre-therapy values.

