 - CNS infection events will be reviewed by an independent medical monitor for whether or not the event meets the criteria above and will be used to calculate this endpoint (Number of subjects meeting CNS infection definition/Number of subjects in the Safety Population)

Secondary Efficacy endpoints:

- Mean reduction of RBCs and total protein by CSF sample post study therapy
 - This calculation utilizes the pre-Neurapheresis sample (first CSF sample taken either at the time of needle insertion or after catheter placement, whichever laboratory value is greater) as compared to the post-Neurapheresis sample (last CSF sample taken prior to catheter removal)

- Mean length of Neuro ICU stay
 - Mean length of Neuro ICU stay will be calculated by two different methods, one using physical location change, the second using criteria for critical care monitoring.

Exploratory endpoints:

- Proportion of subjects requiring additional CSF management during study therapy or on-going CSF management post study therapy
- Reduction in biomarkers of inflammation as seen in CSF, blood and physiologic manifestations post study therapy
 - Such as cytokines, white blood cell counts, neutrophil/lymphocyte ratio, SIRS
- Proportion of subjects with symptomatic complications from aSAH
 - Such as hydrocephalus, clinical vasospasm and delayed cerebral ischemia
- Analysis of endpoints by the following sub-groups for any groups that have at least 5 subjects that meet the criteria for the group;
 - Age: <45, ≥45-<60, 60 – 70 years
 - Gender: male, female
 - Enrollment Modified Fischer grade: 2, 3, 4
 - Baseline cisternal Hijdra score: ≤15, 16-20, 21-25, 26-30
 - Neurapheresis time: <16hrs, ≥16-32hrs, >32-48hrs, >48hrs
 - Other sub-groups not yet defined

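### Exploratory inflammation endpoint: the venous baseline may predate clipping or coiling, and CSF white-cell counts, if used, are not corrected for blood

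*Combined protocol and SAP*

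**What the plan says.** Section 10.2 lists as an exploratory endpoint "Reduction in biomarkers of inflammation as seen in CSF, blood and physiologic manifestations post study therapy", followed by the examples "Such as cytokines, white blood cell counts, neutrophil/lymphocyte ratio, SIRS". It does not say which marker belongs to CSF and which to blood, names no baseline sample for this endpoint, and gives no formula.

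On venous blood, section 7.1 states: "A venous blood sample is also required for screening and to establish baseline values for certain inflammatory markers". It names platelets and white cells, including neutrophils and lymphocytes. Section 5.2 states: "Screening for potential study subjects can be done either prior to or after aneurysm securement". Table 4 requires a blood count with differential at screening, during therapy (36 hours, and 72 hours or end of dwelling) and at 2 days. It has none at catheter placement. Section 7.5.8 takes the during-therapy samples "to allow for comparison to pre-therapy values", without tying those values to a time after securement.

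On CSF, Table 3 in section 7.5.7 specifies "Cell counts with Differential: RBC, WBC, neutrophils, lymphocytes, etc" for the first sample and repeats cell counts with differential at every later one. Red and white cells are thus counted together throughout. Nothing in the plan corrects the white cells for blood.

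**The concern.** The study has a single arm, so each marker is read as change from baseline with no control group to absorb other causes. Two such causes are left open.

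First, a craniotomy or coiling procedure can lie between the venous baseline and every follow-up value. The plan expects this route: the Synopsis allows consent before securement so that the catheter can be placed in the same session, and section 7.4 prefers insertion straight after securement. Section 7.2 requires a post-securement CT baseline because securement can alter the blood seen on CT. The blood count has no equivalent rule.

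Second, the system is built to remove blood cells from CSF. White cells that entered with the haemorrhage can be expected to fall with the red cells, whether or not inflammation changes. A fall in the raw CSF count could then be reported as an anti-inflammatory effect when it partly repeats the secondary red-cell endpoint.

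**Working it through.** **1. Venous baseline: the route through the plan**

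- Baseline is the screening sample (7.1).
- Screening may come before or after securement (5.2).
- The next required count is during therapy, at 36 hours or at end of dwelling if earlier (7.5.8, Table 4).

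A subject sampled before securement can therefore follow the plan exactly and have no count between the procedure and therapy start. The size cannot be computed, because the documents give no venous white-cell data and no share of subjects sampled before securement. PILLAR (section 2.1) shows only that the procedure varies: 5 of 14 clipped (35.7%) and 9 of 14 coiled (64.3%).

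**2. CSF: the plan's own red-cell figure**

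Section 2.1 (PILLAR, N=13) gives mean CSF red cells of 2.78e5 before and 1.17e5 cells/uL after therapy. Percent decrease of means = 1 − 1.17e5/2.78e5 = 57.9%, which matches the stated value.

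**3. Blood-borne white cells**

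Assume one blood-borne white cell per k red cells, with k = 500 to 1000. The documents give no ratio.

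- k = 500: 2.78e5/500 = 556/uL before and 1.17e5/500 = 234/uL after, a fall of 322/uL.
- k = 1000: 278/uL before and 117/uL after, a fall of 161/uL.

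**4. Apparent fall in the total count with inflammation unchanged**

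Let T be the non-blood white cells per uL, held constant. T is also an assumption.

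Apparent fall = [(2.78e5 − 1.17e5)/k] / [2.78e5/k + T]

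| T (/uL) | k = 500 | k = 1000 |
|---|---|---|
| 0 | 322/556 = 57.9% | 161/278 = 57.9% |
| 500 | 322/1056 = 30.5% | 161/778 = 20.7% |
| 1000 | 322/1556 = 20.7% | 161/1278 = 12.6% |
| 2000 | 322/2556 = 12.6% | 161/2278 = 7.1% |

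The top row is the red-cell percentage carried over. It holds only if every CSF white cell came with the blood.

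**5. Masking**

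On the same assumptions, a true rise in non-blood white cells of 322/uL (k = 500) or 161/uL (k = 1000) would leave the raw count unchanged.

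**The case against.** The strongest reply concerns the CSF part. Section 10.2 does not assign white-cell counts to CSF. Read in order, its two lists pair CSF with cytokines, blood with white cells and the ratio, and physiologic manifestations with SIRS. Section 7.4.1 labels the CSF biomarker aliquot as cytokines, Table 3 lists biomarkers separately from cell counts, and section 7.1 ties white cells to the venous sample. This stands: the CSF part is conditional. It is not idle, because the wording does not exclude CSF white cells and every CSF sample yields them.

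A reader might infer that the endpoint as a whole mainly tracks red-cell removal and surgery. The documents do not support that. They contain no CSF white-cell, venous white-cell or cytokine data. The CSF artefact does not reach venous counts or SIRS, and nothing shows how far it touches cytokines. A CSF neutrophil/lymphocyte ratio does not change merely because both cell types are cleared in proportion. The two problems also need not add up: if the procedure raises white cells (an assumption), a pre-securement baseline works against showing a reduction, opposite to the CSF effect.

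It is also fair to say that the endpoint is exploratory in a study without a hypothesis-based endpoint. Section 2.2 records 16 subjects already treated, so a newly required draw could reach at most 30 − 16 = 14 of the 30. That argues for reusing existing counts rather than against the change.

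**Conclusion.** The venous point holds on the text. The plan permits a baseline taken before clipping or coiling and requires no later pre-therapy count. In those subjects, a change in venous white cells or the ratio cannot be credited to therapy alone. Size and direction are unknown, and subjects sampled after securement are unaffected.

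The CSF point holds only if CSF white cells are used as an inflammation marker. The part of the fall due to blood clearance then runs from about 58% (no non-blood cells) to about 7 to 13% (2000/uL). This rests on 500 to 1000 red cells per white cell, a constant non-blood count, and the PILLAR red-cell means. PILLAR capped pump time at 24 hours, so the fall in this study may differ.

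The consequence is limited to how an exploratory result is read. The change is still worth making, because it needs little beyond data already collected.

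**What to change.** In section 10.2:

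1. State which markers apply to CSF, to blood and to physiologic signs.
2. Take the venous baseline as the last available blood count with differential after securement and before therapy start. Use routine ICU counts, including for subjects already treated. Keep the screening value for eligibility.
3. Where no such count exists, keep the screening value as baseline and flag whether it was drawn before or after securement. Show results by that timing and by clip or coil.
4. Where CSF white cells are reported, show beside the raw count a corrected count: CSF WBC − (venous WBC × CSF RBC / venous RBC), using the venous count nearest in time. Describe a fall in the raw count as cell clearance, not as reduced inflammation.

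The cost is analysis wording, retrieval of routine counts where sites have them, and a recorded draw time relative to securement. No new draw is required. The correction can over-subtract if white cells have degraded and under-subtract if red cells have lysed, so it should be a sensitivity display beside the raw count. The timing and procedure groups will be small and should be shown descriptively.

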10.3 Data Management

A 21 CFR Part 11 compliant electronic data capture platform will be used for this clinical study and as such, subject clinical data will be entered into the study database by investigational site staff. All changes made to the clinical data will be captured in an audit trail and available for review by MNeuro or its Monitoring representative.

Unique user ID and password will be provided to each database user by MNeuro or the database vendor as determined by contract. Investigators will be required to review and sign off on the data entered for each of their study Subjects. Sites will not have visibility to study data for any other site participating in the study.

Manual and automatic queries will be issued to the site for appropriate response and clarification of data. Site staff will be responsible for resolving all queries generated by the Sponsor and making source documentation available for each change as applicable.

11. MONITORING

A study initiation visit shall be conducted by the Sponsor and/or their representative to ensure but not limited to:

- Current and completed required study documents are on file;
- Training and associated documentation is complete;
- Site staff understand the requirements of this study protocol;
- The site is prepared for study enrollment

MNeuro will provide notification to the site once they have been approved to enroll subjects. IRB approval is a required element for enrollment approval however sites are not authorized to begin enrollment until they receive notification from MNeuro, regardless of having IRB approval in place.

Clinical monitoring will be performed during the study to assess continued compliance with the protocol and applicable regulations. In addition, the Clinical Monitor will verify that study records are adequately maintained, that data are reported in a satisfactory manner with respect to timeliness, adequacy and accuracy, and that the Investigator continues to have sufficient staff and facilities to conduct the study safely and effectively. The Investigator/institution guarantees direct access to original source documents by MNeuro personnel, their designees, and appropriate regulatory authorities. It is important that the Investigator and relevant study personnel are available during on-site monitoring visits or audits and that sufficient time is devoted to the process.

12. SUSPENSION OR EARLY TERMINATION OF THE INVESTIGATION

MNeuro reserves the right to terminate the study at any stage. MNeuro will exercise this right only for valid scientific, safety or administrative reasons and, reasons related to protection of Subjects. Investigators and their associated IRB will be notified in writing in the event of study termination.

Possible reasons for premature study termination include, but are not limited to:

- The occurrence rates of AE/ UADE that present a significant or unreasonable risk to subjects enrolled in the study
- An enrollment rate far below expectation that prejudices the conclusion of the study
- A decision on the part of Minnetronix to suspend or discontinue development of the device or therapy application.

13. COMPLIANCE

13.1 Statement of Compliance

This study will be conducted in accordance with 21CFR§ 812, International Conference on Harmonisation (ICH) E6 Guidelines for Good Clinical Practice (GCP), ethical principles that have their origins in the Declaration of Helsinki, and pertinent individual country laws and regulations. The study shall not begin until the required approval/favorable opinion from the FDA and the IRB has been obtained. Any additional requirements imposed by the IRB shall be followed.

13.2 Independent Medical Monitor

An independent medical monitor will be utilized for review and adjudication of study reported adverse events. The primary focus of adjudication will be whether the event is anticipated and relatedness to study device or procedure. The medical monitor will be provided available information related to each event such as data from case report forms and copies of de-identified source documents including medical records and imaging studies as applicable. Details related to the responsibilities of the Medical Monitor will be documented in a charter.

Medical monitor adjudication data will be provided to the DSMB for review.

13.3 Data Safety Monitoring Board (DSMB)

Following recommendations outlined in guidance documents on data monitoring committees, the Sponsor has chosen to establish a DSMB safety oversight committee for the PILLAR-XT study. Details related to the responsibilities of the DSMB will be documented in a charter.

The DSMB will be responsible for assessing study stopping (enrollment hold) rules related to the occurrence of the following events:

- Brainstem herniation
- Death
- Early termination of Neurapheresis due to neurological decline in subjects presenting as Hunt & Hess IV
- CSF leak due to device failure

Enrollment will be temporarily placed on hold under the following circumstances;

- if there are two separate occurrences of an individual event listed above or;
 - however, if two separate occurrences of the “early termination of Neurapheresis due to neurological decline in subjects presenting as Hunt & Hess IV” is met, only enrollment of Hunt & Hess IV subjects will be placed on hold.
- if one of the events above is determined by the DSMB to be an unanticipated adverse device effect

The Sponsor will perform an investigation of the event(s) and report to appropriate regulatory authorities. Enrollment may be re-initiated following Sponsor, DSMB and regulatory authority approval. Additionally, the DSMB will review any events determined by the medical monitor to be unanticipated adverse device effects.

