6. RISKS AND POTENTIAL BENEFITS

Subjects participating in this study are exposed to the same inherent risks shared by all patients undergoing treatment for SAH and who receive a lumbar drain as SOC for a number of clinical applications. These risks include but are not limited to headache, nausea/vomiting, transient pain, re-bleed, infection, CSF leak, changes in intracranial pressures, cognitive defects or poor neurological outcomes, other SAH complications and complications from associated interventions (e.g., IA therapy, angiography) and death.

The Study protocol does not prevent SOC for the management of SAH patients and utilizes well established techniques for lumbar puncture for diagnostic purposes, therapeutic applications or interventions. Only Investigators trained in the management of SAH patients, the associated care pathways and/or placement and management of lumbar drains are included in this study. Further, Investigators are trained on the Clinical Protocol to further minimize subject risks.

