6.1 Risks Associated with the Device, Components or Procedure

The table below outlines the risks that are associated with the Neurapheresis System (catheter, components and study procedure). In the event of a catheter or disposable replacement, the risk profile remains unchanged.

Table 2:Neurapheresis System Risks

Risks
Additional radiation exposure
Brainstem herniation
Headache
Nausea / Vomiting
Fluctuation in CSF volume or pressure
CSF leak
Retained catheter
Localized transient pain (back/leg)
Peripheral neuropathy / Paralysis
Re-Bleed / Hemorrhage
Infection / Sepsis
Subdural spinal hematoma
Death

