8.1 Adverse Event Definitions

Adverse Event (AE): Any untoward medical occurrence, unintended disease or injury, or untoward clinical signs in subjects, users or other persons, deemed related to the investigational device (catheter and/or placement accessories), Neurapheresis procedure, or study required element (such as CSF sampling).

Serious Adverse Event (SAE): Adverse event as defined above that

- a) led to death,
- b) led to serious deterioration in the health of the subject, that either resulted in:
 - 1) a life-threatening illness or injury, or,
 - 2) a permanent impairment of a body structure or a body function, or
 - 3) in-patient or prolonged hospitalization, or
 - 4) medical or surgical intervention to prevent life-threatening illness or injury or permanent impairment to a body function,
- c) led to fetal distress, fetal death or a congenital abnormality or birth defect.

Unanticipated Adverse Device Effect (UADE): Any serious adverse effect on health or safety or any life-threatening problem or death caused by, or associated with, a device, if that effect, problem, or death was not previously identified in nature, severity, or degree of incidence in the investigational plan or application (including a supplementary plan or application), or any other unanticipated serious problem associated with a device that relates to the rights, safety, or welfare of subjects" (21 CFR§ 812.3(s)).

Unanticipated Adverse Device Effects (UADE) that occur in subjects enrolled in the clinical trial should be reported under the IDE program (812.150) to FDA and all reviewing institutional review boards (IRBs) and investigators within 10 working days after you first receive notice of the adverse effect(s).

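### The single-event enrolment hold covers only four listed events, so a non-fatal unanticipated device effect outside that list triggers no automatic hold

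*Combined protocol and SAP*

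**What the plan says.** Section 13.3 makes the DSMB responsible for hold rules tied to four events: brainstem herniation; death; "Early termination of Neurapheresis due to neurological decline in subjects presenting as Hunt & Hess IV"; and CSF leak due to device failure. Enrolment is held in two circumstances. The first reads "if there are two separate occurrences of an individual event listed above or"; for the Hunt & Hess IV event, only enrolment of Hunt & Hess IV subjects is then held. The second reads "if one of the events above is determined by the DSMB to be an unanticipated adverse device effect". Restarting needs sponsor, DSMB and regulatory approval.

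The section closes by saying that "the DSMB will review any events determined by the medical monitor to be unanticipated adverse device effects". It attaches no hold to that review.

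Section 8.1 defines a UADE as a serious device-associated effect, problem or death that was "not previously identified in nature, severity, or degree of incidence in the investigational plan" or application. It adds any other unanticipated serious device-associated problem bearing on subjects' rights, safety or welfare.

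Table 2 in Section 6.1 names the device risks. They include "Brainstem herniation", CSF leak and death, and also "Subdural spinal hematoma", paralysis and infection or sepsis, none of which is on the hold list.

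**The concern.** A hold after a single event is most useful for a serious device effect that nobody foresaw. By definition, such an effect is unlikely to be on a list written in advance. Section 13.3 nevertheless requires the event to be on the list and also to be unanticipated. The result is an inverted order: a UADE among the four listed events stops enrolment at once, whereas a non-fatal UADE of an entirely new kind does not.

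The gap matters at this stage. Section 7.5 allows the pump-time limit to be lifted after DSMB review of five subjects, leaving only the 72-hour in-dwelling limit. In PILLAR, pump time averaged about 15 hours and never exceeded 24 (Section 2.1). Effects of longer exposure are among the things the study is meant to reveal, and the trial could go on enrolling through one without breaching any stated rule.

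**Working it through.** The documents give no operating characteristics for the hold rule, so there is no stated figure to reproduce. The one related figure, one herniation SAE in 16 subjects (Section 2.2), is 1/16 = 6.25%, which agrees with the printed 6.3%.

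**Step 1. Listed events against the UADE definition.**

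| Hold event (13.3) | Named in Table 2? | Route to the single-event limb |
|---|---|---|
| Brainstem herniation | Yes | Unexpected severity or incidence |
| Death | Yes | As above, or an unforeseen mechanism |
| CSF leak due to device failure | CSF leak, without the device-failure qualifier | Severity or incidence, or arguably nature |
| Early termination, Hunt & Hess IV | No; Section 6 text mentions "cognitive defects or poor neurological outcomes" | Open under any element of the definition |

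So 3 of 4 events are already named as risks. Each still has a route, because the definition is disjunctive. In the one recorded case, the diencephalic herniation, the event was serious but was tabulated as not unanticipated, so it did not meet this limb.

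**Step 2. An event off the list.** Take a serious, non-fatal device effect that is none of the four and does not lead to one of them.
- Two-event limb: not counted, because it is confined to listed events.
- Single-event limb: not counted, for the same reason.
- Closing sentence of 13.3: DSMB review if the medical monitor calls it a UADE; no hold.

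The probability of a rule-driven hold is therefore 0 whatever the event rate. The same holds for repeated related SAEs off the list, such as non-fatal paralysis, subdural spinal hematoma or meningitis.

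**Step 3. What a wider single-event limb would do.** Subjects still to be treated: n = 30 − 16 = 14 (Sections 4.2 and 2.2). The rates p of off-list UADEs are assumptions; the documents give none. P(at least one) = 1 − (1 − p)^14:

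| Assumed p | (1 − p)^14 | P(at least one) |
|---|---|---|
| 1% | 0.869 | 13% |
| 2% | 0.754 | 25% |
| 5% | 0.488 | 51% |
| 10% | 0.229 | 77% |

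As a guide to the range, the tables in Sections 2.1 and 2.2 show no unanticipated event in 13 + 16 = 29 treated subjects. The one-sided 95% upper bound is 1 − 0.05^(1/29) = 9.8%, so 10% is at the edge of what those data allow. Two cautions apply: the PILLAR-XT table covers the therapy period only, and earlier exposure may have been shorter.

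**Step 4. Repeated related SAEs, for information.** If two occurrences of one off-list type triggered a hold, P(at least two) = 1 − (1 − p)^14 − 14p(1 − p)^13. This gives 0.8%, 3.1%, 15% and 42% at assumed rates of 1%, 2%, 5% and 10%. The figures are per type. For four independent types at 5% each, the chance of at least one hold is 1 − (1 − 0.153)^4 = about 49%.

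**The case against.** A reader might infer that the single-event limb is empty, or could almost never operate. The documents do not support that. Section 8.1 lets a named risk qualify on severity or degree of incidence and has a further catch-all. Death is listed, so a fatal UADE can meet the limb. Early termination in Hunt & Hess IV subjects is not a Table 2 risk, and naming it as a hold trigger does not make it an anticipated device effect. One herniation recorded as not unanticipated shows that the limb was not met once, not that it cannot be met. Nor is there any count to show that the hold misses most events in the second primary endpoint: the only related SAE tabulated is a herniation, which is at least close in kind to a listed event.

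Other safeguards exist. Section 8.1 sends UADEs to FDA, IRBs and investigators within 10 working days. Section 13.2 gives all adjudication data to the DSMB. Section 7.5.2 has the sponsor told immediately when therapy is terminated for a listed reason, including paralysis and spinal hematoma. Section 12 allows the study to be terminated on AE or UADE rates. The DSMB charter, which was not available, may add rules.

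All of this stands, and it limits the point to the absence of an automatic hold. It does not close the gap: each of these safeguards is either a reporting duty or a discretionary decision without a threshold, and Section 13.3 is where the protocol sets out when enrolment is held.

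**Conclusion.** The point holds in a limited form. As Section 13.3 is written, a non-fatal UADE outside the four listed events gets DSMB review and no automatic enrolment hold, while a UADE among the listed events does stop enrolment. The chance of a rule-driven hold for the off-list event is exactly 0, which follows from the text and needs no assumption. The 13% to 77% range for a wider rule rests on assumed UADE rates of 1% to 10%, independence between subjects, and 14 subjects remaining. The conclusion also assumes that the charter, not seen here, contains no broader hold.

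The lack of a hold for repeated related SAEs off the list is a separate matter. The documents give no basis for a particular threshold, and the chance of extra holds grows with the number of event types counted, so it is a question for the sponsor and DSMB rather than a defect with one evident remedy.

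**What to change.** In Section 13.3, reword the second circumstance so that enrolment is held when any event, whether or not it is on the list, is judged a UADE by either the medical monitor or the DSMB. Naming both bodies also removes the present split, in which the DSMB makes the determination for the hold and the medical monitor makes it for the review. Align the DSMB charter.

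The cost is one clause in the protocol, a matching charter edit, and an occasional extra temporary hold. That hold is reversible, but it lasts until the sponsor, DSMB and regulator agree to restart. At an assumed 1% off-list UADE rate the chance of such a hold over the remaining 14 subjects is about 13%.

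Separately, the sponsor and DSMB should state whether repeated related SAEs outside the list, for example paralysis, subdural spinal hematoma or meningitis, are meant to trigger a hold. If so, they should choose the rule with its chance of extra holds in view. No threshold is proposed here.
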